11.1.2 Pharmacokinetic Variables

The PK characteristics of RV521 to be assessed will be: C_{max} , AUC_{0-12} , AUC_{0-t} , $t_{1/2}$, $AUC_{0-\infty}$, CL/F , V/F and C_{12} (data permitting), and in addition for Part B: accumulation ratio, percent fluctuation, AUC_{tau} , C_{ave} , C_{min} (C_{trough}) as well as any other relevant parameters.

Pharmacokinetic analysis will include listings and summaries of PK concentrations by time point, derived PK, parameters and analysis of relationship with dose and body weight.

Data regarding exposure after accumulation will be compared to parameters observed in adult subjects (C_{max} , AUC_{tau} , C_{12} [data permitting]) with the application of a possible safety factor.

11.1.3 Pharmacodynamic Variables

Pharmacodynamic variables include individual viral loads (by RT-qPCR) and/or CBIA if available at each sampling time point, percent change from baseline for 60 and 156 hours after first dose as well as other additional PD parameters may be also considered as PD endpoints.

For Parts B and C, the DAVG statistic (time-weighted average change in RSV viral load), for both total RSV viral load by RT-qPCR and RSV viral load by CBIA, will be calculated as:

$$DAVG = \frac{\sum_{i=a}^b 0.5 (Y_i + Y_{i+1}) (t_{i+1} - t_i)}{t_b - t_a}$$

Where Y_i is the change from baseline in \log_{10} RSV viral load at time point i , t is the actual time at the specified time point, a is the baseline assessment at Dosing Visit 1, and b is the last assessment on Follow up Day 7.

Pharmacodynamic parameters, including the viral load, AUC, and any other PD parameters which are derived, will be summarised by treatment (dose level). For Parts B and C, comparisons will be made between RV521 and placebo using analysis of covariance models. Data will be log transformed as appropriate.

The primary analysis in Part C will be the time-weighted average change in nasopharyngeal RSV viral load which will be calculated from baseline (Day of Randomisation) to Day 7 and compared across treatment groups. An analysis of the RSV viral load in the presence and absence of other known respiratory pathogens will be performed. This analysis will be outlined in the SAP.

Secondary virology endpoints derived from the RSV viral load as measured in nasopharyngeal swabs will include but are not limited to:

- Change from baseline in viral load (RT-qPCR and CBIA) at each time point
- Time to below viral load quantification limit (RT-qPCR and CBIA)

- Proportion of subjects with viral load below quantification limit (RT-qPCR and CBIA) at each timepoint throughout the study

CCI [REDACTED]
[REDACTED]
[REDACTED]
[REDACTED]
[REDACTED]

Note: the key analysis will pool subjects with both RSV A and RSV B. However, selected analyses will be repeated for the RSV A and RSV B subgroups separately.

Further details of the analyses will be provided in the SAP.

11.1.4 CCI [REDACTED]

[REDACTED]
[REDACTED]
[REDACTED]
[REDACTED]
[REDACTED]
[REDACTED]
[REDACTED]
[REDACTED]
[REDACTED]
[REDACTED]
[REDACTED]

11.1.5 Clinical Response Variables

Two scales of clinical response will be considered, the RSV Clinical Scoring System and the ReSViNet scale. In Parts A and B, clinicians will complete the RSV Clinical Scoring System, which gives a score from 0 to 12. In Part C, the ReSVinet scale for clinicians, which gives a score from 0 to 20 will be completed. For parental assessment of clinical response, the Adapted Version of ReSVinet Scale for Parental Use, which gives a score from 0 to 20 will be analysed.

Both the RSV Clinical Scoring System and the ReSViNet scale for clinicians will be summarised by treatment (dose level) and time point. In addition, for post-dose assessments, change from baseline will also be summarised, where baseline is the last non-missing score prior to the first dose of study drug. For Parts B and C, comparisons will be made between RV521 and placebo using analysis of covariance models.

In addition the score for the RSV Clinical Scoring System will be categorised as:

- Mild – scores ≤ 5
- Moderate – scores > 5 and < 9
- Severe – scores ≥ 9

The number and percent of subjects with mild, moderate and severe assessments will be summarised by treatment (dose level and time point).

The Adapted Version of ReSVinet Scale for Parental Use score will be summarised by treatment (dose level) and time point. In addition, for post-dose assessments, change from baseline will also be summarised, where baseline is the last non-missing score prior to the first dose of study drug. For Part B and Part C, comparisons will be made between RV521 and placebo using analysis of covariance models.

Individual RSV-related signs and symptoms ([Appendix 17.4](#)) at each visit will be summarised by treatment (dose level). Quantitative variables will be summarised using the statistics number of observations (n), mean, SD, median, minimum and maximum values. In addition, change from baseline will also be summarised for post-baseline visits. Baseline will be defined as the last non-missing result before the first dose of study medication. Qualitative variables will be summarised using n (number of subjects), absolute numbers and relative frequencies (%) per class.

Time to improvement will be calculated for RSV-related signs and symptoms that are classified as moderate or severe during the course of the study and will be defined as the time from randomisation until no longer present (absent) or mild.

The Overall Time to Improvement will be defined as the time from randomisation to the time that all RSV-related signs and symptoms are mild or absent. The overall time to improvement will be summarised for each treatment group by mean, median, SD, minimum and maximum and 95% confidence intervals.

Overall Time to Resolution of RSV-related signs and symptoms will be calculated from the time of randomisation to the time that they are no longer present (absent), and will be summarised and analysed as for Time to Improvement.

Treatment groups will be compared for differences in overall severity assessed by the composite symptom score on each day whilst hospitalised and at follow-up visits.

For Part C, time to resolution of symptoms will be compared between each dose level of RV521 and Placebo using a generalised Wilcoxon Rank test. Details of the analysis will be provided in the SAP.

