8.4.2 Inclusion Criteria

To be eligible for study entry subjects must satisfy all of the following criteria at the Screening Visit:

1. Male or female \geq 1 month and \leq 36 months of age.
2. Weigh \geq 3.5 kg (Parts A, B, and C) but \leq 18 kg (Part C only).
3. Clinical diagnosis of LRTI defined by
 - a. Evidence of respiratory infection by one or both of the following with or without fever
 - i. Rhinitis/coryza
 - ii. Cough
 - AND
 - b. Evidence of LRTI by the presence of one or more of the following:
 - i. Increased respiratory rate PLUS other evidence of lower respiratory tract disease (eg, laboratory or radiographic evidence)
 - ii. Increased respiratory effort as evidenced by one or more of the following:
 1. Grunting with expiration
 2. Nasal flaring
 3. Retraction: intercostal or subcostal
 - iii. Wheezing: audible or on chest auscultation
4. A positive RSV diagnostic test (RSV infection confirmed either according to routine site practice [polymerase chain reaction or diagnostic quick test], or using a [Sponsor-provided] commercial kit).
5. Hospitalised because of RSV LRTI (bronchiolitis or bronchopneumonia).
6. For Part B, symptoms of LRTI must be present for no more than 1 week before the Screening Visit, with the first day of symptoms counting as Day 1.
7. For Part C, symptoms of LRTI must be present for no more than 5 days prior to Screening Visit, with the first day of symptoms counting as Day 1.
8. Expected to remain in the hospital for minimum of 3 days (administration of 6 doses) for Part B only.
9. The parent(s)/legal guardian(s) of the subject have provided written informed consent for the subject to participate.

10. The parent(s)/legal guardian(s) are able and willing to comply with the study protocol.

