10.1.3.7 Vital Signs

Vital signs (body temperature, systolic and diastolic BP, oxygen saturation, HR, RR, and pulse oximetry) will be recorded at the time points specified in the relevant Schedule of Assessments for Part A (Table 1), Part B (Table 2) and Part C (Table 3a inpatients and Table 3b outpatients).

In Part C, collected vital signs and SpO₂ levels will be analyzed as normal, mild, moderate, or severe according to the following definitions:

- Temperature:
 - Normal (no fever): <38°C
 - Mild: 38-39°C
 - Moderate: >39-40°C
 - Severe: >40°C
- Respiratory rate (breaths/min):
 - Normal: ≤30
 - Mild: 31-45
 - Moderate: 46-60
 - Severe: >60
- SpO₂ on Room Air (Oxygen Saturation)
 - Normal: >94%
 - Mild: >92-94%
 - Moderate: 90-92%
 - Severe: <90%

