## 8.3. RSV-related Signs and Symptoms

RSV-related signs and symptoms (temperature, respiratory rate, coryza, cough, grunting with expiration, nasal flaring, retractions, wheezing and SpO2 on Room air) will be collected on the CRF at each time point identified in the Schedule of Assessments for Part B (Table 2), and Part C (Table 3) in Section 3.10.

For study Parts B and C, assessments of individual RSV-related signs and symptoms will be summarised at each time point. For quantitative variables, observed values and changes from baseline will be summarised. In addition, highest level of severity during the study for each individual RSV-related sign and symptom will be summarised using summary statistics for categorical variables.

Time to improvement will be calculated for RSV-related signs and symptoms that are classified as moderate or severe during the course of the study and will be defined as the time from randomisation until no longer present (absent or severity=0) or mild. If there is no improvement, then time to improvement will be censored as the date/time RSV-related signs and symptoms were last recorded. Time to improvement will be summarised (number [%] of subjects analysed, mean, median, SD, minimum, maximum) for Parts B and C. The overall time to improvement will be defined as the time from randomisation to the time that all RSV-related signs and symptoms are mild or absent. The overall time to improvement will be summarised for Parts B and C by n, mean, median, SD, minimum, maximum and 95% confidence intervals for the mean. For Part C only, time to improvement of symptoms and overall time to improvement, will be compared between RV521 and Placebo using a Generalised Wilcoxon analysis, which is a weighted log-rank test, weighted by the number of subjects at risk immediately prior to the event, and will include duration of symptoms prior to randomisation as a covariate. Also for Part C only, Kaplan-Meier plots for time to improvement of symptoms and overall time to improvement will be presented by treatment.

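### Overall time to improvement has no baseline severity condition, so an infant whose signs are all mild or absent at entry counts as improved at or near time zero

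*Protocol*

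**What the plan says.** Protocol 11.1.5 has the endpoint "defined as the time from randomisation to the time that all RSV-related signs and symptoms are mild or absent". SAP 8.3 repeats it: "the time from randomisation to the time that all RSV-related signs and symptoms are mild or absent". Neither adds a condition on severity at baseline or a rule for later worsening. The SAP's censoring sentence deals only with infants who never reach the state: "If there is no improvement, then time to improvement will be censored as the date/time RSV-related signs and symptoms were last recorded".

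The neighbouring endpoints do carry conditions. For single signs, Protocol 11.1.5 says "Time to improvement will be calculated for RSV-related signs and symptoms that are classified as moderate or severe during the course of the study", although that condition refers to any time in the study and not to baseline. SAP 8.3 limits time to resolution to signs present at the start.

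For Part C, SAP 8.3 compares overall time to improvement "using a Generalised Wilcoxon analysis, which is a weighted log-rank test, weighted by the number of subjects at risk immediately prior to the event", with duration of symptoms before randomisation as a covariate.

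On entry, Protocol 8.4.2 asks for cough or coryza plus "Evidence of LRTI by the presence of one or more of the following". Wheeze heard only through a stethoscope is enough, and no sign needs a minimum grade. Appendix 17.4 lists nine items. Coryza, cough, retractions and wheeze have a mild grade; grunting and nasal flaring are only none or present; the other three are measurements, for which Protocol 10.1.3.7 says "In Part C, collected vital signs and SpO₂ levels will be analyzed as normal, mild, moderate, or severe".

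Protocol 7.2 makes time to improvement a secondary endpoint of Part C. SAP 4.4, written for a 1:1 Part C of about 120 infants, lists it as primary.

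**The concern.** The event is a state, and an infant can already be in that state at randomisation. Such an infant has nothing to improve from, so its event time says nothing about RV521. The rule also scores an infant who is mild at entry, severe on Day 2 and recovered on Day 6 as an immediate success. LRTI symptoms may have begun up to 5 days before screening, so illness can still be progressing at entry.

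The chosen test makes this worse. A generalised Wilcoxon test weights each event time by the number still at risk, which is everyone at time zero. A chance imbalance between arms in the number of all-mild infants therefore enters at the greatest weight and can mask a real difference among the others.

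**Working it through.** **1. Can an all-mild infant enrol?** Take mild cough, mild wheeze on auscultation, respiratory rate 42, SpO₂ 94%, no fever, and no retractions, grunting or flaring.

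- Protocol 8.4.2: cough plus wheeze meets the LRTI criterion.
- Protocol 10.1.3.7: a rate of 31-45 is mild, SpO₂ above 92% and up to 94% is mild, and a temperature below 38°C is normal.
- Overall rule: every item is mild or absent, so the endpoint is met at the pre-dose record, or at the first 12-hour record if pre-dose does not count. The documents do not say which.

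**2. The plan's own figure.** No power is stated for this endpoint. The stated 34 per group is for viral load (Protocol 11.2: difference 1, SD 1.25, 90% power, two-sided 0.05). The normal formula gives n = 2 × (1.960 + 1.282)² × 1.25² / 1² = 32.8, so 33. The t-test gives 33.8, so 34, with 90.2% power. The figure reproduces and does not depend on the definition at issue.

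**3. Why time-zero events matter.** The statistic sums n × (d₁ − d × r₁/n) over event times, where n is the number at risk, d the events, and d₁ and r₁ the events and number at risk in the treated arm. With 34 per arm and m₀ and m₁ all-mild infants, the time-zero term is 68 × (m₁ − (m₀ + m₁)/2) = 34 × (m₁ − m₀). A chance imbalance of one infant moves the statistic by 34.

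**4. Size of the loss, by simulation.** Inputs from the documents:

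- 34 evaluable per arm, two-sided 0.05 (Protocol 11.2).
- Median 4 days, IQR 3 to 7.5 (SAP 3.7). Log-normal sigma = ln(7.5/3) / (2 × 0.6745) = 0.679. This matches the ratio of the quartiles. With the median at 4 it puts them at 4/√2.5 = 2.5 and 4 × √2.5 = 6.3 days.
- The SAP's generalised Wilcoxon test, here without its covariate.

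Assumptions: a share q of each arm is all-mild at entry; RV521 shortens the time by 30% or 40% in the rest; signs are recorded every 12 h to day 4.5, then on days 7, 14 and 34. SAP 3.7 uses 30%, but for time to resolution. There were 8,000 simulated trials per cell.

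| q | 30% shorter: as written | all-mild excluded | loss | 40% shorter: as written | all-mild excluded | loss |
|---|---|---|---|---|---|---|
| 0 | 53.6% | 53.6% | 0 | 84.4% | 84.4% | 0 |
| 2% | 51.2% | 53.5% | 2.3 | 81.1% | 83.6% | 2.5 |
| 5% | 46.1% | 52.2% | 6.1 | 75.1% | 82.0% | 6.9 |
| 10% | 38.6% | 50.0% | 11.4 | 64.5% | 79.6% | 15.1 |
| 20% | 26.9% | 45.6% | 18.7 | 46.2% | 74.8% | 28.6 |
| 30% | 18.1% | 41.3% | 23.2 | 29.4% | 68.9% | 39.5 |

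A second set of 8,000 gave losses of 11.9 points (38.1% vs 50.0%) at q = 10% and 19.8 points (25.8% vs 45.6%) at q = 20% for the 30% effect, so these cells are good to about a point.

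**5. Variations.**

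- Scoring the all-mild infants at 12 h instead of time zero gives 38.6% in the same cell (q = 10%, 30% effect).
- An ordinary log-rank test with these infants kept gives 42.9% at q = 10% and 35.4% at q = 20% (30% effect), so part of the loss comes from the weighting.
- With no treatment effect and these infants kept, the rejection rate is 4.9%, 5.2% and 4.8% at q = 0, 20% and 40%.

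**The case against.** The strongest objection is that the share is unknown and may be small. These infants are in hospital because of RSV LRTI, and all nine items must be mild or absent. Grunting or flaring alone rules an infant out. The respiratory-rate grades are not adjusted for age: 46-60 is moderate in Protocol 10.1.3.7, while the clinicians' ReSVinet scale treats 40-50 as normal under 2 months, so a young infant can fail the all-mild test at a normal rate. This stands, and it is why the size can be given only as a range.

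Second, the calculation takes its sample size from the current protocol and its test and median from a SAP written for another Part C design. Protocol 11.1.5 names the Wilcoxon test only for time to resolution, and Protocol 11.1 allows SAP amendments before lock and unblinding. This also stands. It makes the figures illustrative, but the definition itself is in both documents.

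Third, the overall endpoint could be read as inheriting the per-sign condition, so that an always-mild infant never enters. The text does not say so. That reading would also select infants on severity after randomisation, which treatment can affect.

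Fourth, worsening is visible elsewhere: highest severity, the daily composite score and change in ReSVinet are all reported. That is true, but it does not correct this endpoint.

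**Conclusion.** The point holds as a fault in the definition of a secondary endpoint. As written, an eligible infant with all signs mild or absent at entry is an immediate success whatever follows. Under the assumptions above, the loss of power against excluding such infants is about 2 to 3 points at a 2% share, 6 to 7 at 5%, 12 to 15 at 10% and 19 to 29 at 20%.

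A reader might infer that the endpoint's power is bound to collapse. The documents do not support that: they give no share, and the loss is small if few infants are all-mild. Even with none, power for a 30% reduction is only about 54%, so this comparison is weak for other reasons too. A reader might also infer false-positive findings or a threat to the trial's 90% power. Neither follows: type I error stays near 5%, and the viral-load sample size is unaffected.

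**What to change.** In Protocol 11.1.5 and the Part C SAP, define and test overall time to improvement in infants with at least one sign moderate or severe, or grunting or nasal flaring present, at the last assessment before Dose 1. This subset is fixed before treatment, so the randomised comparison is preserved within it. Report separately, by arm, how many infants were all-mild at that assessment and how many of them later became moderate or severe. A blinded count of all-mild infants before lock would show which row of the table applies.

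I would not add a rule that improvement must hold for 24 h or to the next visit. Once an infant is discharged the next record may be days or weeks away (Days 7, 14 and 34), so the confirmation period would depend on discharge, which happens after randomisation. If sustained improvement is of interest, use a sensitivity analysis that does not depend on discharge status.

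The cost is wording only, since the data are already collected. Somewhat fewer infants contribute: at a 10% share, 34 × 0.9 = 30.6, or about 31 per arm. Prevention of progression in initially mild infants is then described alongside this endpoint instead of within it.

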Part A: Subjects will participate for up to 8 days, and the visit schedule will include:

Screening Visit (-24 hours to first dose), Dosing Visit 1 (-2 hours pre-dose to 18-24 hours post-dose), Post-dosing Visit 2 (48 hours post-dose), and a Telephone Follow-Up (Day 7).

Part B: Subjects will participate up to 13 days, and the visit schedule will include:

Screening Visit (-24 hours to first dose), Dosing Visit 1, Dosing Visit 2, Dosing Visit 3, Dosing Visit 4, Dosing Visit 5, Follow-Up 40-48 hours Post-Dose 10 (Visit Day 7) and a Telephone Follow-Up (Day 12).

Part C: Subjects will participate for up to 35 days, and the visit schedule will include:

Screening (-24 hours to first dose), Dosing Visits 1-5, Follow-Up 40-48 hours Post-Dose 10 (Visit Day 7) and additional follow-up on Day 14 and Day 34. Inpatient duration will be determined clinically by the PI or other health care provider. Follow-Up days are expected to be on an outpatient basis.

Study Population:Inclusion criteria:

To be eligible for study entry, subjects must satisfy all of the following criteria at the Screening Visit:

1. Male or female ≥ 1 month and ≤ 36 months of age.
2. Weight ≥ 3.5 kg (Parts A, B and C) but ≤ 18 kg (Part C only).
3. Clinical diagnosis of LRTI defined by
 - a. Evidence of respiratory infection by one or both of the following with or without fever:
 - i. Rhinitis/coryza
 - ii. CoughAND
 - b. Evidence of LRTI by the presence of one or more of the following:
 - i. Increased respiratory rate PLUS other evidence of lower respiratory tract disease (eg, laboratory or radiographic evidence).
 - ii. Increased respiratory effort as evidenced by one or more of the following:
 1. Grunting with expiration
 2. Nasal flaring
 3. Retraction: intercostal or subcostal
 - iii. Wheezing: audible or on chest auscultation
4. A positive RSV diagnostic test (RSV infection confirmed either according to routine site practice [polymerase chain reaction or diagnostic quick test], or using a [Sponsor-provided] commercial kit).
5. Hospitalised because of RSV LRTI (bronchiolitis or bronchopneumonia).
6. For Part B, symptoms of LRTI must be present for no more than 1 week before the Screening Visit, with the first day of symptoms counting as Day 1.
7. For Part C, symptoms of LRTI must be present for no more than 5 days prior to the Screening Visit, with the first day of symptoms counting as Day 1.
8. Expected to remain in hospital for minimum of 3 days (administration of 6 doses) for Part B only.

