9.4.5 Post Treatment (Part C)

Visit Day 7 (40 – 48 Hours Post-Dose 10) Follow-up:

Note: Visit Day 7 may occur on Study Days 7 or 8 depending on when the subject received his or her first dose of IMP.

- Physical examination
- Evaluation of hydration status
- Body weight/length/head circumference
- Vital signs (body temperature, systolic and diastolic BP, HR, RR)
- 12-Lead ECG
- Record RSV-related signs and symptoms, and severity (if indicated), including: temperature, cough, coryza, grunting with expiration, nasal flaring, retractions, and wheezing
- ReSVinet scale for clinicians ([Appendix 17.6](#))
- Adapted ReSVinet Scale for Parental use ([Appendix 17.2](#))
- Safety laboratory tests (clinical chemistry and haematology)
- Urinalysis
- PK blood sample according to sampling schedule in [Table 5](#)
- Nasopharyngeal swab
- Concomitant medication review
- Adverse event review

Visit Day 14 Follow-up:

- Vital signs
- Body weight/length/head circumference
- Record RSV-related signs and symptoms, and severity (if indicated), including: temperature, cough, coryza, grunting with expiration, nasal flaring, retractions, and wheezing
- ReSVinet scale for clinicians ([Appendix 17.6](#))
- Adapted ReSVinet scale for parental use ([Appendix 17.2](#))
- Nasopharyngeal swab
- Concomitant medication review
- Adverse event review

Visit Day 34 Follow-up:

- Vital signs
- Body weight/length/head circumference
- Record RSV-related signs and symptoms, and severity (if indicated), including: temperature, cough, coryza, grunting with expiration, nasal flaring, retractions, and wheezing

- ReSVinet scale for clinicians ([Appendix 17.6](#))
- Adapted ReSVinet scale for parental use ([Appendix 17.2](#))
- Nasopharyngeal swab
- Concomitant medication review
- Adverse event review

Early Withdrawal (or Discontinuation) Visit

Parents/legal guardians who withdraw their child from the study will be encouraged to allow their child to complete the same final evaluations as subjects completing the study according to this protocol (ie, at the relevant post-treatment visit), particularly safety evaluations.

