9.5 Duration of Treatment

Part A:

Subjects will participate for up to 8 days. A single oral dose of RV521 will be administered in Part A, and the visit schedule will include:

- Screening Visit (-24 hours)
- Dosing Visit 1 (-2 pre-dose to 18-24 hours post-dose)
- Post-dosing Visit 2 (48 hours post-dose)
- Telephone Follow-up (Day 7)

Part B:

Subjects will participate for up to 13 days. The proposed dosing regimen for Part B is RV521 or placebo administered BID, 12 hours apart, for a period of 5 consecutive days (for a total of 10 doses), and the visit schedule will include:

- Screening Visit (-24 hours)
- Dosing Visit 1 (-2 to 18-24 hours post-dose)
- Dosing Visit 2
- Dosing Visit 3
- Dosing Visit 4
- Dosing Visit 5
- Follow-Up Visit Day 7 (+40-48 Hours Post-Dose 10)
- Telephone Follow-Up (Day 12)

Note: The actual day of each Dosing Visit will be dependent upon the time that the subject receives their first dose of IMP on Visit 1. Follow-Up Visit Day 7 may therefore fall on Study Days 7 or Day 8 depending upon the time the subject received his or her first dose of IMP on Dosing Visit 1.

Part C:

Subjects will participate for up to 35 days, and the visit schedule will include: Screening (24 hours to first dose), Dosing Visits 1 to 5 (5 days), and follow-up 40-48h Post-Dose 10 (Study

Days 7 or 8) and at Study Days 14 and 34. Inpatient duration will be determined clinically by the PI or other health care provider and by ability to complete study procedures and assessments on an outpatient basis ([Section 9.4](#)). Follow-up days are expected to be on an outpatient basis.

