### **Part C**

Part C is a double-blind and placebo-controlled study, enrolling 1 cohort (Cohort 6) of approximately 120 subjects ( $\geq 1$  month to  $\leq 36$  months of age). After a parent/legal guardian provides informed consent, and conditional to satisfactory fulfilment of all inclusion criteria and none of the exclusion criteria (as for Parts A and B), subjects will be randomised 1:1 to receive RV521 or matching placebo. RV521 or placebo will be administered according to the dose and regimen specified for the age group following completion of Part B/ Cohort 5 subjects. Subjects will be followed for safety and tolerability. Clinical findings related to RSV infection will be monitored. The DSMC will evaluate safety data at intervals specified in the DSMC Charter. Nasopharyngeal swabs will be obtained over the course of the study period to evaluate viral load, presence of other respiratory pathogens and CCI [REDACTED].

Subjects will participate for 29 days, and the visit schedule will include:

Screening (-24 hours to first dose), Dosing (5 days), and Follow-Up 40-48 hours Post-Dose 10 (Visit Day 7) and Study Days 14, and 28. Inpatient duration will be a minimum of 3 days, with duration determined clinically by the PI or other health care provider. Follow-Up days are expected to be on an outpatient basis.

This document is confidential.

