### 3.7. Determination of Sample Size

Because of the exploratory nature of the study, a formal sample size calculation has not been performed. Twenty-four subjects enrolled in Part B and receiving RV521 or placebo (2:1) at the same dose level and according to the same dosing regimen for their specified age range group are expected to be sufficient to assess safety, PK, and antiviral data.

For an anti-viral effect (Part B), measured as a difference in viral load at a specific time point, and using data from the human challenge model (Study CCI [REDACTED]), 24 subjects split 16/8 would have 69% power to identify a difference of 2 log units, 87% power for a difference of 2.5 log units and 96% power for a difference of 3 log units.

Estimates for total enrolment into Part C are based on a median time to resolution of symptoms (defined as the interval from day randomisation to the day on which all symptoms of RSV are recorded as absent [severity = 0]) of 15 days with inter-quartile range = 9 days (Petruzella et al, 2010). A total sample size of 120 subjects randomised 1:1 (RV521:placebo) yields a power of 80% to detect a reduction in median time to resolution of symptoms of 30% by Generalised Wilcoxon analysis and assuming a drop-out rate of 15%. Median time to improvement is defined as the interval from day randomisation to the day on which symptoms of RSV present at study entry are recorded as mild or absent (severity =0) and is estimated to be 4 days (IQR = 3 to 7.5 days) (Mansbach et al, 2015).

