Time to resolution will be calculated for RSV-related signs and symptoms that are present at study start and will be defined as the time from randomisation until no longer present (absent or severity=0). If there is no resolution, then time to resolution will be censored as the date/time RSV-related signs and symptoms were last recorded. The overall time to resolution will be defined as the time from randomisation to the time that all RSV-related signs and symptoms are no longer present (absent or severity=0). The time to resolution and the overall time to resolution will be summarised and analysed as for time to improvement.

Times to improvement or resolution will be presented in days to 1 decimal place.

All tables for Part C, will also be presented by the subgroups defined in Section 6.6.

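### Part C time to resolution is interval-censored across widely spaced visits, so medians, means and differences in days will be set by visit dates

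*Protocol*

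**What the plan says.** **Schedule.** The Protocol synopsis gives Part C a Visit Day 7 and "additional follow-up on Day 14 and Day 34". At each of these visits section 9.4.5 asks sites to "Record RSV-related signs and symptoms, and severity (if indicated), including: temperature, cough, coryza" and the other listed signs. Nothing that records the sign list is scheduled between Day 14 and Day 34. In Table 3a and section 9.4.4 the records at Doses 7 to 10 are taken only while the infant is in hospital, so an infant discharged after Dosing Visit 3 has no sign-list record until Visit Day 7. Infants discharged before Dosing Visit 3 do have daily records (Table 3b). SAP version 2.0, section 3.5, has a different last visit: "Visit Day 7) and Study Days 14, and 28".

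**Analysis.** Protocol section 11.1.5 reports overall time to resolution by mean, median, SD, range and 95% confidence interval, and for Part C adds that "time to resolution of symptoms will be compared between each dose level of RV521 and Placebo using a generalised Wilcoxon Rank test". SAP section 8.3 says that time to resolution "will be defined as the time from randomisation until no longer present (absent or severity=0"). It right-censors at the last record, adds Kaplan-Meier plots for Part C, and gives times to one decimal of a day. Neither document has a rule for an event that happens between visits.

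**Expected course.** SAP section 3.7 assumes a median time to resolution "of 15 days with inter-quartile range = 9 days", "defined as the interval from day randomisation to the day on which all symptoms of RSV are recorded as absent".

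**The concern.** If signs are present at one visit and absent at the next, the data show only that resolution lies somewhere between the two. With no other rule, the programmed event time is the date of the later visit. When visits are a day apart this hardly matters. When they are 20 days apart and the expected median sits just after the first of them, it decides the result: an event on day 15 and one on day 32 both enter the analysis as day 33.

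Time to resolution is a named secondary clinical endpoint in the current Part C, and a difference in days is the figure most likely to be carried forward as an effect size. A median or mean that reflects the appointment calendar would mislead whoever plans the next trial, even if the p-value is sound.

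**Working it through.** **Inputs.** Median 15 days, IQR 9 and a 30% reduction (15 × 0.7 = 10.5 days): SAP 3.7. Study day counts randomisation as Day 1 (SAP 6.2), so Day 14, Day 28 and Day 34 are 13, 27 and 33 days after randomisation. Visit Day 7 is 40 to 48 hours after Dose 10. With 12-hourly dosing Dose 10 falls at 108 hours, so the visit falls at 148 to 156 hours, about 6.4 days. Group size: 34 evaluable per arm (Protocol 11.2, set for viral load).

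**The plan's own figure.** SAP 3.7 claims 80% power with 120 subjects; 60 × 0.85 = 51 per arm after dropout. It names no survival distribution. An exponential gives 44%, a normal 91% to 93%, a lognormal 98%. The figure is not reproduced, but without the distribution it cannot be called wrong, and nothing below depends on it.

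**Share of placebo resolutions in the last gap.** Four distributions were fitted to median 15 and IQR 9.

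- Normal: SD = 9/1.349 = 6.67. P(13 < T ≤ 33) = Φ(18/6.67) − Φ(−2/6.67) = 0.997 − 0.382 = 0.614 (before rounding).
- Lognormal: 15(e^(0.6745σ) − e^(−0.6745σ)) = 9 gives σ = 0.438. P = Φ(ln(33/15)/0.438) − Φ(ln(13/15)/0.438) = 0.964 − 0.372 = 0.592.
- Weibull (shape 2.57) and log-logistic (shape 3.72) likewise.

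| | Days 13–33 | Days 14–34 | Days 13–27 | Days 14–28 | Days 13–33, true median 10 |
|---|---|---|---|---|---|
| Normal | 61.4% | 55.7% | 58.2% | 53.4% | 32.6% |
| Weibull | 61.3% | 55.6% | 57.5% | 52.8% | 25.7% |
| Lognormal | 59.2% | 53.2% | 53.8% | 48.5% | 27.2% |
| Log-logistic | 57.9% | 51.8% | 52.9% | 47.4% | 26.2% |

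Columns 1 and 2 are the Protocol's schedule under the two ways of counting days; columns 3 and 4 are the SAP's Day 28 schedule. In the last column the normal keeps its SD and the others keep their shape.

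**What would be reported.** Each event is dated to the first scheduled record at or after it, with all dosing-period records assumed present.

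- True placebo median 15: recorded median 33 days in about 89% to 91% of trials with 34 per arm (normal, lognormal), and 13 days, or the midpoint 23, in nearly all the rest. The mean delay is about 9.5 days over all events and about 14 days for events in the gap (normal).
- True median 10.5: recorded median 13 days. A true difference of 15 − 10.5 = 4.5 days is shown as 33 − 13 = 20.
- True median 13: close to a coin-flip between 13 and 33.
- True medians 10 and 7 (also a 30% cut), lognormal: at median 10, P(T > 13) = 1 − Φ(ln(1.3)/0.438) = 0.27; at median 7, P(T > 6.4) = 1 − Φ(ln(6.4/7)/0.438) = 0.58. Both expected medians are recorded at 13, so a true 3-day difference is shown as 0.

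**Effect on the test** (Gehan-Wilcoxon, 1,500 simulated trials per scenario). Type I error is 4.4% to 5.9% on the visit schedule and 4.6% to 5.9% with daily records. Power at 34 per arm for a 10.5-day median falls from 89% to 82% (lognormal) or from 77% to 69% (normal).

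**Time to improvement.** SAP 3.7 gives median 4 days, IQR 3 to 7.5. Lognormal σ = ln(7.5/3)/1.349 = 0.679; P(T ≤ 5) = Φ(ln(5/4)/0.679) = 0.63. About 63% of improvements fall within the dosing period, where records are 12-hourly in hospital or daily for early discharges.

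**The case against.** **The 15-day figure belongs to another design.** It appears only in SAP version 2.0, whose Part C is 1:1 with 120 subjects, a Day 28 visit and symptom resolution as a primary endpoint. The current Part C is 1:1:1 with 111 subjects and is powered on viral load. This stands, and is why the Day 28 columns are shown. The cited source is also titled as a duration-of-illness study. If its 15 days ran from onset (an assumption, since the SAP says randomisation), entry with up to 5 days of symptoms could put the median near 10 days and the share in the gap near 26% to 33%. A reader might therefore infer that most placebo recoveries go unobserved. The documents support only a narrow majority, conditional on the SAP's figure. For true medians from 10 to 15 days, however, the recorded median is still almost always a visit date or the midpoint of two.

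**The times are not wrong by the SAP's definition.** Section 3.7 counts to the day on which absence is recorded. A reader might call the reported times errors; late and coarse is the fair description.

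**The comparison is not invalid.** Both arms share the schedule, so the test keeps its size. A reader might infer a biased test; the simulation does not show one.

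**Details are deferred.** Section 11.1.5 leaves them to the SAP, and section 11.1 allows amendments before database lock and unblinding. That shows where to make the change. It does not supply the missing rule.

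**Other records exist.** The parental ReSVinet scale continues at home, but its items omit cough and coryza, so it cannot date the point at which all signs are absent.

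**Conclusion.** The point holds for estimation, not for testing. Followed as written, the plan reports Part C time to resolution to a tenth of a day from visits 20 days apart (14 in the SAP), and the medians, means and Kaplan-Meier steps will largely reproduce the visit dates. The distortion can run either way: a 4.5-day difference can appear as 20, and a 3-day difference as 0.

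The size of the gap share rests on the SAP's 15-day median running from randomisation and on fitted curves. That the recorded median is set by a visit date does not rest on the 15 days; it holds for every true median examined from 10 to 15 days. The results assume complete dosing-period records. Infants discharged after Dosing Visit 3 lack some of these, which would coarsen the data further. Time to improvement is much less affected and should not be put on the same footing.

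**What to change.** In the Part C SAP amendment:

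1. For estimation, treat time to resolution as interval-censored, from the last visit with any sign present to the first visit with all absent. Give the Turnbull estimate per arm in place of the visit-dated Kaplan-Meier curve, and state the median as the interval in which it lies.
2. Report the proportion resolved by Day 7, Day 14 and Day 34 per arm, with confidence intervals for the differences from placebo. As a guide to precision, the lognormal case at Day 14 gives 37.2% v 68.7%. With 34 per arm the standard error is √(0.372 × 0.628/34 + 0.687 × 0.313/34) = 0.115, so the 95% interval is about ±22.5 points.
3. Drop visit-dated means, SDs and differences in medians.
4. Keep the generalised Wilcoxon test.
5. Apply the same handling to time to improvement only for events after the dosing period.
6. State the last visit as in the current Protocol (Day 34), since SAP version 2.0 still has Day 28.

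The cost is SAP wording and a little more analysis, with no new visits or samples. The price is wider and coarser estimates, which is what these visits can support.
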